3.2 Analysis

3.2.1 Summary of Principal Outcome Variables and Regression Variables

Variables

- Primary outcome: Patient treatment success by six months (see MOP, Section 2.6)
- Patient treatment success at twelve months (Phase I)
- Successful control of inflammation in both eyes by twelve months, with complete discontinuation of corticosteroids
- Best spectacle-corrected visual acuity, at baseline and at the time of failure or six months (two observations per patient)
- Time to corticosteroid sparing control of inflammation (6 months and 12 months)
- Change in health related quality of life subscores (PCS and MCS) from SF-36 and Vision Related Quality of Life from NEI-VFQ-25 and IND-VFQ at six months and twelve months

- Reason for discontinuation of therapy (if applicable) at six months and twelve months
- Macular thickness at baseline, and at six months and twelve months
- Presence of macular edema at six months and twelve months
- Vitreous haze assessed clinically by the NEI and Davis scales at baseline, six months, and twelve months
- Vitreous haze as assessed by the photographic grading of haze by the NEI and Davis scales at baseline six months and twelve months
- The proportion of patients discontinuing due to serious adverse events at six months and twelve months
- Tabulate the occurrence of dose reduction used in immunosuppressive treatment.
- Treatment efficacy of VKH patients at six months and twelve months
- Treatment efficacy of patients with vasculitis at enrollment

Note that the presence of cataracts renders assessment of vitreous haze more difficult. Vitreous haze measurements in the presence of certain cataracts will be considered less reliable, and this will be considered in statistical modeling. Analyses will be repeated for differing assumptions about this bias. A maximum likelihood latent variable model will be considered, in which a true underlying vitreous haze level predicts an observed value. The observation model will include a higher probability of yielding a large observed value in the presence of a cataract.

Major independent variable of interest

- Treatment assignment (methotrexate or mycophenolate mofetil)

Additional regression variables used in selected analyses

- Anatomic location (coded dichotomously as either intermediate (code 0) or as being either posterior uveitis or panuveitis (code 1))
- Country
- Study site
- Gender
- Age
- Baseline quality of life (health and vision related)

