categories: anterior/intermediate or intermediate only, and posterior/panuveitis). Anatomical location by history is considered the prespecified analysis; anatomical location at enrollment will supplement this finding.

We propose to proceed as follows. We propose to begin with Equation (1), adding terms $\beta_3 X_i^3 + \beta_{13} X_i^1 X_i^3$ for anatomic location and for treatment-location interaction. We wish to test the hypothesis that $\beta_{13} = 0$, i.e. that there is a difference in treatment efficacy between the anatomic locations, controlling for country. Alternative models will be fit in which the country, site, and treatment x country terms are omitted.

We will also report relative risks in each substratum, using relative risk regression.

Additional analyses will add gender and age to the predictors. The entire analysis will be repeated for each gender, and separately for each country (US and India) and anatomic location.

Planned Secondary Analyses.

Each of the following secondary analyses is designed to test the hypothesis that treatment assignment affects a given outcome, after controlling for selected covariates. All analyses will be repeated without controlling for covariates (i.e., using treatment assignment as the only predictor). In all cases, appropriate regression diagnostics and/or goodness of fit tests will be performed (further details are given below). In addition, we will compute jackknife influence statistics in each analysis, to determine whether or not any single observation (eyes or patients, as appropriate) have an undue effect on the final conclusion. All models with site effects will be repeated omitting this effect, and again repeated including a treatment-site effect, and with country and/or treatment by country interactions (i.e., pooling within countries when appropriate). When reporting findings, care will be taken to distinguish the single prespecified test from supplemental tests (whether prespecified or unprespecified); exploratory analyses will always be labeled as such. All alpha levels are to be two-sided.

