1. *Twelve-month endpoint for successes.* We propose to compare the proportion who maintain successful control for twelve months (i.e. the outcome is the proportion who have achieved control in all study eyes both at the six month visit and at the 12 month visit) between the two study arms. Per protocol, patients with successful control of their inflammation at 6 months remain on the same treatment until 12 months. We will use the same statistical model (and Wald procedure) as for the primary analysis. We test the hypothesis that the coefficients for treatment assignment and treatment assignment/anatomic location interaction both equal zero.

2. *Time to corticosteroid sparing control of inflammation.* We propose to use a Cox proportional hazard model with the outcome being the time to (1) first steroid-sparing control, and separately (2) first control of inflammation, with treatment assignment (and interaction) as the predictors. Time to first steroid-sparing control is the principal prespecified analysis here; alternative approaches will be conducted for additional insight and as sensitivity analyses. We will supplement this analysis with a parametric survival analysis using the Weibull distribution and also with a gamma distribution (note that individuals may drop out at any time, not just at the monthly visits), and with a method treating the time to success as interval censored. The outcome for this analysis is a single number for each patient (not for each eye). The primary statistical

result will be the Wald test for the treatment assignment coefficient. We will repeat the analysis using study site as a fixed effect in this model (and as a sensitivity analysis, will explore random-effects survival analytic methods which are becoming available, see Pankratz et al.).⁶ In supplementary analyses we will include age and anatomic location as additional covariates.

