3.4.2 Power for Subgroup Analyses and Other Analyses

Subgroups in Specific Aim 1.

The prespecified subgroup analysis for specific aim 1 is to examine the difference between the methotrexate and mycophenolate mofetil groups within each anatomic location. Using Equation (5), we anticipate having in excess of 80% power to detect a difference of 25% in success rates.

The power for selected secondary outcomes is provided here.

Secondary Outcomes in Specific Aim 1.

1. *Twelve-month endpoint for success.* We assume an additional loss of 5% between 6 and 12 months (that is, in addition to the 10% already lost to follow-up in the first six months). **We expect approximately 78% power to detect a 20% difference in success rates at the 12-month endpoint.**

2. *Time to corticosteroid sparing control of inflammation.* For sample size planning, we use the approximate formula given in Friedman et al (2010) for the number in each group:

$$N = \frac{(Z_\alpha + Z_\beta)^2 (\phi(\lambda_C) + \phi(\lambda_I))}{(\lambda_I - \lambda_C)^2}$$

where λ_C is the hazard in the methotrexate group, λ_I is the hazard in the mycophenolate mofetil group, and $\phi(u) = \frac{u^2}{1 - e^{-uT}}$

where T is the censoring time (6 months). Previous studies suggest a median success time of approximately 3.5 months for mycophenolate mofetil.¹² **Assuming a 10% loss to follow-up, 108 subjects in each group provides 80% power to detect a difference of 2.47 months in the expected difference.** (Note: λ_C is $\log(2)/3.5$ mo. for this calculation.) We assume an alpha of 0.05 (two sided).

3. *Change in BSCVA.* For sample size planning, we assume a T-test comparing change scores between the two drugs, assuming a standard deviation of the change in visual acuity of 6.5 letters.^{13, 14} The sample size of 108 will provide approximately 80% power to detect 2.63 letters of difference in the change score. In other words, **we expect to have 80% power to detect whether mycophenolate mofetil yields 2.63 letters more of improvement than methotrexate, and we will have greater power to detect greater differences.** The power formula is provided in Chow et al and is computationally implemented in R in the function `power.t.test` (which we used).¹⁵

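### Time to steroid-sparing control: the lead Cox test is the treatment coefficient alone in a model that also holds an unnamed interaction, so it does not test the overall drug effect that the SAP describes and powers

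*Combined protocol and SAP*

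**What the plan says.** SAP 3.2.2 (Specific Aim 1, Planned Secondary Analyses), item 2, plans a Cox model "with treatment assignment (and interaction) as the predictors". Of its two time-to-event outcomes, "Time to first steroid-sparing control is the principal prespecified analysis here". The primary statistical "result will be the Wald test for the treatment assignment coefficient". Item 2 then says: "In supplementary analyses we will include age and anatomic location as additional covariates". It does not say what treatment interacts with.

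Other places bear on the reading:

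- Item 1, directly before, does name an interaction and tests it jointly with treatment: "We test the hypothesis that the coefficients for treatment assignment and treatment assignment/anatomic location interaction both equal zero".
- SAP 3.2.1 lists anatomic location as "coded dichotomously as either intermediate (code 0) or as being either posterior uveitis or panuveitis (code 1".
- The opening of the Planned Secondary Analyses says each one tests whether treatment assignment affects the outcome. It adds: "All analyses will be repeated without controlling for covariates (i.e., using treatment assignment as the only predictor". It also requires reports to separate the single prespecified test from supplemental ones.
- SAP 3.4.2 powers this outcome as a plain two-group comparison of hazards with no interaction term: "We assume an alpha of 0.05 (two sided").

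**The concern.** When a model contains treatment, a 0/1 covariate and their product, the treatment coefficient is the drug effect where the covariate is 0. It is not an average over all patients. A Wald test of that coefficient alone answers a narrower question than the one posed, and the power calculation in SAP 3.4.2 belongs to a different test.

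The wording raises a second problem. If location enters only in supplementary analyses, the lead model holds an interaction without its main effect, and the treatment coefficient can then pick up prognostic differences between locations.

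At stake is how the principal time-to-event result is read. A real drug difference could be missed or, under the second model, a difference could be declared where there is none.

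**Working it through.** **1. The plan's own figure.** Inputs from SAP 3.4.2: 108 per arm, 10% loss (108 × 0.9 = 97.2 evaluable), T = 6 months, one hazard ln2/3.5, two-sided alpha 0.05, 80% power, detectable difference 2.47 months.

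N = (Zα + Zβ)² [φ(λC) + φ(λI)] / (λI − λC)², with φ(u) = u²/(1 − e^(−uT)).

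- λC = ln2/3.5 = 0.1980; φ = 0.0564
- λI = ln2/(3.5 + 2.47) = ln2/5.97 = 0.1161; φ = 0.0269
- N = 7.849 × 0.08328 / 0.006714 = 97.4 evaluable, and 97.4/0.9 = 108.2 enrolled per arm

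The figure reproduces as a difference in medians (3.5 against 5.97 months, hazard ratio 0.586). Power at 97.2 per arm is 79.9%. The SAP quotes 3.5 months for mycophenolate but assigns that hazard to methotrexate. The arm labels do not affect this two-group power figure.

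**2. Location main effect included.** The log hazard ratio is β₁T + β₃L + β₁₃TL, with L = 0 for intermediate. β₁ is the drug effect in intermediate patients, so only they inform it. Put m = 97.2 × (1 − share posterior/pan) into power = Φ(√(m/0.08328) × 0.08194 − 1.96):

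| Posterior/pan share (assumed) | m per arm | Power of the β₁ test |
|---|---|---|
| 30% | 68.0 | 65% |
| 50% | 48.6 | 51% |
| 67% | 32.1 | 36% |

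Cox simulations (97 per arm, exponential times, censoring at 6 months, uniform hazard ratio 0.586) agree within about two points: about 64%, 51% and 37%, against 79–82% for treatment only. Type I error in this model stays at about 5%. If the drug effect exists only in posterior/pan patients (hazard ratio 1.8), the β₁ test still rejects only about 5% of the time.

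**3. Location main effect omitted (literal text).** The log hazard ratio is β₁T + β₁₃TL. All methotrexate patients have value 0, whatever their location. β₁ therefore compares intermediate mycophenolate patients with all methotrexate patients. With no drug effect in either location, one simulation run (2,500 trials per cell) gave these rejection rates:

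| Posterior/pan share | Location HR 1 | HR 0.7 | HR 0.5 |
|---|---|---|---|
| 30% | 5% | 8% | 17% |
| 50% | 5% | 14% | 34% |
| 67% | 5% | 17% | 42% |

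Separate runs gave 10–19% at 0.7 and 18–45% at 0.5, the same picture to within a few points. In all these null settings the treatment-only test rejected about 4–6% of the time.

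**4. Another interaction partner.** If the partner were country (US coded 0 in item 3), β₁ would be the US effect. SAP 6.2.3 projects 15 and 30 American patients at one third and two thirds of the trial, hence about 45 of 216 by extrapolation. Then m = 97.2 × 45/216 = 20.3, and the formula in step 2 gives about 25% power.

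**The case against.** Item 2 does not identify its interaction, and location is described there as an additional, supplementary covariate. Reading a location interaction into the lead model is an inference from item 1. That stands, and the location-specific figures are conditional on it. The basic defect is not: with any 0/1 partner, the lone treatment coefficient is not the overall effect, as step 4 shows.

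A reader might infer that the lead test both covers one anatomic group and gives false positives. The documents do not support joining the two. They belong to different models: the first has the main effect and holds its type I error, and the second lacks it and is not a within-group test. Omitting the main effect is also the less likely intention. Where the SAP writes a location interaction out (the prespecified subgroup analysis, and item 4 on visual acuity), location enters as well. The inflation also needs location to be prognostic, which the documents do not say.

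A reader might also infer that the plan never tests the overall drug effect on this outcome. It does: every secondary analysis is repeated with treatment as the only predictor. But that repeat is supplemental under the SAP's own distinction. If the two results disagree, the SAP points the reader to the less suitable one.

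**Conclusion.** The point holds in limited form. As written, the prespecified lead test for time to steroid-sparing control does not test the overall drug effect that the section describes and the power calculation assumes. Under the likeliest reading, with the location main effect included, the cost is power, not type I error: a fall from about 80% to between about 64% and 37% for assumed posterior/pan shares of 30% to 67%. Inflated false positives are a conditional risk of the literal model only.

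The location shares and location hazard ratios are assumptions; the documents give neither. The simulations also assume exponential times and a uniform drug effect, except where stated.

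This is one secondary outcome. The trial's primary analysis is a one-degree-of-freedom treatment test with no interaction and is unaffected. The point is a should-fix.

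**What to change.** In SAP 3.2.2 item 2, delete the parenthetical mention of an interaction, so that the treatment-only Cox Wald test is the prespecified result. Move the interaction to the supplementary analyses, name its partner, and state that it is always fitted with its main effect. Leave the handling of site as already planned.

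A joint two-degree-of-freedom test in the style of item 1, with the main effect in the model, would also be valid. It has about 72% power at the planned effect against 81–82% for treatment only in the same simulations, so it is the weaker lead.

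The cost is a change to one sentence and one clause added to the supplementary analyses, made before unmasked analysis. No new data are needed, and the treatment-only model is already among the planned repeats.

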2.4 Randomization

2.4.1 Stratification between sites

Patients will be recruited from nine sites: [REDACTED]

[REDACTED] (see Manual of Operations Section 2.2 for details). Patients will be randomized to two treatments (arms): methotrexate (X) or mycophenolate mofetil (Y). The treatment protocols are specified in the FAST Uveitis Trial Manual of Operations.

Within each site, assignments will be conducted using a block randomization scheme with randomly varying block sizes.

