2.4.2 Randomization list

Lists of sequential randomization assignments will be prepared for each site. The randomization lists consist of a unique identifier for each patient, together with the assignments to treatment arms. The assignment of patient ID numbers and randomization is thus performed on enrollment.

The randomization lists for sites will be prepared by the [REDACTED] site (see Section 10.3) and sent to the Emergency contact at each site to be used only in case emergency unmasking is needed for patient safety.

They will also be sent to hospital/clinic staff who are responsible for telling the study coordinators the treatment assignment for each patient after the patient is enrolled and the study ID has been assigned. At these sites she will verify patient treatment assignment as a quality assessment.

A backup copy of the full randomization list for all four sites will be maintained by [REDACTED] [REDACTED] This list will be maintained as a hard copy stored in a locked file cabinet at the [REDACTED] site, and to be used only in case emergency unmasking is needed for patient safety.

Distribution of the randomization list to [REDACTED] will be accomplished using the [REDACTED] encrypted email provision. Email is encrypted using the Advanced Encryption Standard (NIST FIPS 197) whenever the first four characters of the subject line are PHI: The sender is notified when the recipient receives a secure email; the recipient receives a notification of a secure email and can view it using the [REDACTED] Secure Messenger website. We have successfully used this method in previous clinical trials [REDACTED] [REDACTED]. The randomization lists will each contain more randomization assignments than needed. Successively recruited patients will receive sequential

assignments from the list. The long list provides a measure of added safety in case one of these sites recruits far more patients than expected relative to the other site.

As discussed below, the randomization lists will be provided as Excel® worksheets. No technical knowledge will be required to use these lists.

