The primary analysis is a logistic regression with treatment arm as a predictor. For the primary analysis, we propose to use study site as a *random effect* (random intercept model). The null hypothesis is that the regression coefficient for treatment arm equals zero, which will be tested using a likelihood ratio test with one degree of freedom. We will also fit the following models: (a) a model including drug, site, and drug \times site interaction, (b) a model including only drug and site, (c) a model including only drug and country, and (d) a model with drug, country, drug-country interaction, and site within country. Countries or sites with fewer than three observations will be pooled together. Provided there is no evidence of treatment \times site interaction or treatment \times country interaction, we will report pooled treatment effects and confidence intervals. In the event evidence suggests a difference between treatment sites, we will report treatment effects by site, and repeat the analysis excluding particular sites. Similarly, evidence of a treatment \times country interaction will lead us to report treatment effects and confidence intervals by country.

Simulations suggest that use of a model containing interaction terms between site or country and treatment for the primary analysis is undesirable. Such a procedure results in modest loss of power unless the treatment effect is of opposite sign in different sites or countries.

The hypothesis test is to be two-sided with alpha of 0.05. We propose to compute the P-value by permutation testing, based on the block randomization scheme.

Prespecified Subgroup Analysis.

The prespecified subgroup analysis will test the hypothesis that there is a treatment effect separately in each anatomic group, using a logistic regression model.

We denote the two anatomic groups by X_i^3 , which equals 0 when the patient is in the intermediate group and 1 when the patient is in the posterior/pan group. In the intermediate subgroup, we plan to determine whether there is evidence of a treatment effect (regardless of the effect in the posterior/pan group). Specifically, we will conduct this analysis in two ways: anatomical site at enrollment (split into three categories: anterior, anterior/intermediate or intermediate only, and posterior/panuveitis), and anatomical location by history (split into two

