3. *Country and site within country.* We denote the country by X_i^2 , which will be 0 for US locations and 1 for Indian locations; X_n^4 is 1 only for patients in the second Indian site and 0 otherwise, while X_{iz}^4 is 1 only for patients in the second US site and 0 otherwise. As mentioned under the Primary analysis, we propose to fit models with country only, drug by country interaction, and with a drug by country interaction, including site within country as well. Analysis will be conducted within each site, then pooling the sites within country together. Further details regarding pooling across centers are provided above under the main prespecified analysis.

4. *Best spectacle-corrected visual acuity (BSCVA).* The primary outcome variable for this secondary outcome will be the change in best spectacle-corrected visual acuity from baseline to final (as defined in the FAST MOP, i.e. for those who successfully control inflammation as defined in the MOP, or at the time of failure for those who fail; MOP, Section 2.6). Visual acuity change scores are available for both eyes for each patient.

The primary analysis will use a linear mixed-effects regression, where the outcome variable is the change in BSCVA in each eye, using treatment assignment as a statistical predictor (regressor, independent variable); a random effect will be used at the individual level, because of the possibility that changes in the two eyes from a given patient are correlated. In a supplementary analysis, we will include as predictors (independent variables) anatomic location of uveitis, interaction between anatomic location and treatment assignment, and the study site, together with a random effects for patient. We will fit these models using maximum likelihood (R procedure `lmer`) and use likelihood-ratio tests to test the hypothesis that treatment assignment affects BSCVA change. Only eyes that are eligible and meet inflammation criteria at baseline will be included in this analysis. If at a given visit, vision cannot be assessed, we will carry the last observation forward. Additional sensitivity analyses for missing data will be used (including mixed effects models controlling for time, including all data from an individual).

Also, if there is no eye at Month 6 to assess, the patient will be given a logMAR value of 2.0.

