3.9 Accrual Rate

Based on enrollment rates in previous trials and preliminary data (see proposal for details) we anticipate enrolling 7-8 subjects per month at all sites, for a total enrollment period of 2.5 years. If we conservatively assume we may only accrue 25% fewer subjects per month, then completion of enrollment would occur 3 years and 3 months after the start of the trial.

We will establish monthly recruitment goals for each of the sites, taking into careful consideration local holidays which may cause recruitment rates to drop at certain times of the

year. Careful monitoring of the recruitment process will enable us to determine whether one of our sites may be falling behind in recruitment, precursory to further investigation and intervention. Standard graphs of realized cumulative recruitment together with cumulative recruitment goals for (a) the study as a whole, and (b) for each of the four sites will be prepared, and provided to the Data and Safety Monitoring Committee at each meeting (or more frequently, if requested).

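### The site-within-country model in SAP 3.2.2 item 3 has codes for four sites although the trial recruits from nine, so five sites are merged with a reference site in that supplementary model

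*Combined protocol and SAP*

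**What the plan says.** SAP 2.4.1 gives the current number of centres: "Patients will be recruited from nine sites".

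SAP 3.2.2, under the primary analysis of Specific Aim 1, enters study site as a random effect ("random intercept model"). It then lists four further models:
- (a) drug, site and their interaction;
- (b) drug and site;
- (c) drug and country;
- (d) "a model with drug, country, drug-country interaction, and site within country".

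Sites or countries with fewer than three observations are pooled. A pooled effect is reported if there is no evidence of a treatment-by-site or treatment-by-country interaction.

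Item 3 of the planned secondary analyses in 3.2.2 supplies the coding for the country and site-within-country models. The country variable is one "which will be 0 for US locations and 1 for Indian locations". The first site variable "is 1 only for patients in the second Indian site and 0 otherwise". The second "is 1 only for patients in the second US site and 0 otherwise". Item 3 also plans analyses within each site and refers back to the primary analysis for the details of pooling across centres.

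**The concern.** Two site indicators, one per country, fit a trial with two sites in each country. This trial has nine sites. An analyst who follows item 3 as written fits a model that is called site within country but separates only four groups. Patients at the remaining five sites are treated as if they belonged to the reference site of their country. An analyst who notices must depart from the SAP without written guidance on how. Either way, item 3 does not specify the analysis it names.

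What is at stake is small: the adjustment for site in model (d), and any repeat of that model with a treatment-site term. The introduction to the planned secondary analyses says that models with site effects will be repeated with such a term. Read literally, that takes the four-site coding into an interaction model as well.

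**Working it through.** The plan derives no figure on this point, so the check is a count.

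**Inputs**
- Sites: 9 (SAP 2.4.1).
- Country indicator: 2 levels, US = 0 and India = 1 (SAP 3.2.2, item 3).
- Site indicators: 2, one for the second Indian site and one for the second US site (same item).

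**Distinct codes.** The possible values of (country, second Indian site, second US site) are:
1. US reference: (0, 0, 0)
2. Second US site: (0, 0, 1)
3. Indian reference: (1, 0, 0)
4. Second Indian site: (1, 1, 0)

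That is 4 codes, and 9 − 4 = 5 sites have none of their own.

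**Does the split between countries matter?** Site names and locations are redacted. Let there be u US and v Indian sites, with u + v = 9 and at least two in each country, as item 3 itself presupposes. The number merged is (u − 2) + (v − 2) = 9 − 4 = 5. So five sites are merged under every split from 2 + 7 to 7 + 2.

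**Degrees of freedom**

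| Term | All nine sites coded | As coded in item 3 |
|---|---|---|
| Country | 1 | 1 |
| Site within country | (u − 1) + (v − 1) = 7 | 2 |
| Total | 8 | 3 |
| Treatment by location, if the model is repeated with a treatment-site effect | 8 | 3 |

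The shortfall is 7 − 2 = 5 site indicators, before any pooling of sites with fewer than three observations.

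**Chosen or left over?** Nothing in the SAP says that five sites are to be merged by design. The only merging rule in 3.2.2 is the one for fewer than three observations. The revision history (SAP section 11) logs the change to nine sites on 13 January 2015 for 2.4.1, and a matching change to the patient identifiers in 2.4.4. The only change it logs for 3.2.2 is the added non-inferiority analysis. Four-site wording also survives elsewhere: 2.4.2 has "A backup copy of the full randomization list for all four sites", 3.9 plans recruitment graphs "for each of the four sites will be prepared", and 2.4.6 again counts four. A missed update is the natural explanation.

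**Which models use this coding?**
- Primary model: site as a random intercept, with no reference to the item 3 indicators. Not affected.
- Models (a) and (b): site entered as such. Not affected as written.
- Model (c): drug and country only. Not affected if all sites are in the US or India.
- Model (d): country and site within country, which is what item 3 codes. Affected in its site main effects. Its drug-by-country term remains in place, but the adjustment for site around it is incomplete.

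**The case against.** The strongest reply is that this is stale notation with no consequence for the trial's conclusions. Most of that stands. The treatment-by-site part of the pooling rule rests on model (a), which uses site itself. Model (d) has no drug-by-site term, so correct coding would not make it a test of treatment by site. Item 3 also plans analyses within each site. If sites differ, 3.2.2 provides for effects by site and for repeating the analysis without particular sites.

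A reader might infer more: that differences at five sites are hidden from the check that decides whether results are pooled. The opening of the primary analysis may encourage this, because it speaks broadly of heterogeneity of sites or countries. The documents do not support that reading. The same section goes on to state the rule in terms of treatment-by-site and treatment-by-country interaction, and no section makes a test of site within country a condition for pooling. For the same reason, any power calculation for a site main-effect test would describe a test that the SAP does not use for this decision.

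What the reply does not remove is the mismatch itself. Item 3 cannot be carried out as a site-within-country analysis of nine sites, and the within-site analyses do not repair the model.

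One uncertainty remains. The SAP cites an Equation (1) that is not in the supplied text, so whether its site term used the same coding cannot be checked. That is no evidence of a wider fault.

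**Conclusion.** The point holds as a minor specification error confined to one supplementary model. Item 3 distinguishes four sites where there are nine, so five are merged with a reference site. Site within country has 2 degrees of freedom instead of 7. The same applies, read literally, to the repeat of that model with a treatment-site effect. The primary test, the treatment-by-site check in model (a) and the rule for reporting pooled effects stand as written.

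The count of five assumes that all nine sites are in the US or India, with at least two in each. A site elsewhere would have no defined country code. The documents name no third recruiting country (3.2.2 lists the countries as US and India), but site locations are redacted, so this cannot be settled from the text.

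**What to change.** - In SAP 3.2.2, item 3, replace the two site indicators with one term per site nested in country, covering all nine sites. Keep the existing rule that sites with fewer than three observations are pooled.
- State once that *site* in models (a), (b) and (d), and in their repeats with a treatment-site effect, means all nine sites.
- Add a level to the country variable only if a site lies outside the US and India.
- Correct the remaining four-site wording in 2.4.2, 2.4.6 and 3.9 at the same time.

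The cost is a SAP wording change and at most five more site parameters in a supplementary model (somewhat more in its repeat with a treatment-site effect). Sample size, data collection and the primary analysis do not change.
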